We propose a prospective, randomized protocol of non-inferiority in order to compare the two new strategies to the reference strategy for the detection of advanced neoplasia. (1st arm: OC first; 2nd arm: CC first, OC at 3 years for those patients with negative initial CC; 3rd arm: annual FIT for 2 years (t_0 , $t = 1$ year, $t = 2$ years), colonoscopy at 3 years for those patients with negative FIT during the study). The strategies will be considered to be equivalent if the 95% confidence interval of the different rate of detected advanced neoplasia won't exceed $\pm 3\%$.

HYPOTHESIS

We make the hypothesis that the results of the two study groups (colon capsule endoscopy and fecal immunological test) will be non-inferior to the results of the control group (optical colonoscopy).

OBJECTIVE

Main objective

To demonstrate the non-inferiority of CC and FIT to OC in terms of efficacy for the detection of advanced colorectal neoplasia (adenoma > 1 cm or with high grade dysplasia, or colorectal cancer any stage).

Secondary objectives

1. Efficacy of each strategy for the detection of colorectal cancer
2. Safety and complications of each screening strategy
3. Cost-effectiveness analysis of the 3 strategies

METHODOLOGY

Study design

Non inferiority multicenter prospective randomized 3 arm study.

We propose a 3 arms prospective, randomized protocol evaluating the sensitivity of 3 strategies for the diagnosis of colon and rectum cancer and advanced neoplasia:

- 1st arm: OC first
- 2nd arm: CC first, OC at 3 years for those patients with negative initial CC
- 3rd arm: annual FIT for 2 years (t_0 , $t = 1$ year, $t = 2$ years), colonoscopy at 3 years for those patients with negative FIT during the study.

The strategies will be considered to be equivalent if the 95% confidence interval of the difference or the detection of advanced neoplasia won't exceed $\pm 3\%$.

Evaluation criteria

Evaluation criteria -> Main objective

The primary endpoint is the prevalence of advanced colorectal neoplasia (adenoma > 1 cm, adenoma with high grade dysplasia) or cancer identified by each strategy after 3 years (expected frequency with the reference examination, *i.e.* colonoscopy: 5,6 %).

Evaluation criteria -> Secondary objectives

The secondary endpoints are:

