1. Rate of colorectal cancer identified by the 3 different strategies/interval cancers (yearly clinical follow-up and interval colonoscopy), or cancers detected at the end of the 3 years by control colonoscopy in arm 2 and 3
2. Percentage of patient experienced a significant complication from any screening strategy
3. Cumulative costs of each strategy compared to the detection of advanced neoplasia/cost per advanced neoplasia detected and cost/life-years gained
4. Quality assessment of colonoscopy and capsule endoscopy (rate of completion of colonoscopy and capsule endoscopy, caecal intubation rate).

Study population

Patients at high risk of colorectal cancer (first degree relatives of patient with colorectal cancer) will be included prospectively in one of the 3 comparative arms.

Inclusion criteria

- History of colorectal cancers (any age) in first-degree relatives (parents, children, siblings including half-brothers and sisters)
- Age \geq 45 years
- No previous colorectal cancer screening
- Informed patient
- Patient having signed the consent form,
- patient affiliated to a social security system or recipient of such system

Exclusion criteria

- Any previous colorectal cancer screening
- Any known advanced neoplasia or colorectal cancer
- Known genetic predisposition to colorectal cancer (very high risk group)
- Adults protected by law (under guardianship or curatorship)
- Other metastatic cancers
- Life-threatening diseases
- History of blood tests in the stool (hemocult, fecal immunological test, ...)
- History of colonic capsule screening
- History of colonoscopy

Implemented techniques

Colonoscopy: OC will be performed as usual for each institution, either out-patient or in-patient, with a split preparation, under general anesthesia, without modification of the usual procedure.

Fecal Immunochemical Testing: we will use the OC Sensor test, with a cut-off 10 μ g Hb/gr of stool, without modification of the usual procedure.

Colon capsule endoscopy will be realized by experienced teams with a standardized bowel preparation, usual reading by gastroenterologists, and without modification of the usual procedure.

Number of patients required

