Patient follow-up

- 1st arm: OC first, then annual follow-up for 3 years by phone call.
- 2nd arm: CC first, yearly follow-up for 3 years by phone call, OC at 3 years for those patients with negative initial CC.
- 3rd arm: annual FIT yearly for 2 years (t_0 , $t = 1$ year, $t = 2$ years) and yearly follow-up for 3 years by phone call, OC at 3 years for those patients with negative FIT during the study.
- Pathological examination of detected and resected colorectal neoplasia will follow the usual conditions of pathological examination. There will be no centralized pathological analysis.

Measured parameters

The following data will be recorded: number and age of the index case(s) with colorectal cancer; number, size and dysplasia of neoplastic colorectal lesions; toxic habits (tobacco, alcohol); BMI; type of familial link (parent, offspring and siblings) with the index case; pathological characteristics of neoplastic lesions. Quality assessment of colonoscopy and capsule endoscopy (caecal intubation rate; capsule completion rate with rectal visualization and capsule excretion).

Blinding

Pathological analysis of colorectal lesions will be performed blindly.

Supply of medical devices

The colon capsules needed for the study will be graciously provided by MEDTRONIC, which will deliver them directly to the reference centers upon demand.

The FIT kits needed for the study will be graciously provided by MAST DIAGNOSTIC, which will dispatch them to the reference centers upon demand.

FIT analysis will be carried out by the Laboratory of Functional Coprology (Pitié-Salpêtrière Hospital) on a measuring device and with reagents both graciously provided by MAST DIAGNOSTIC.

STATISTICAL ANALYSIS

1. Descriptive analysis

The quantitative characteristics of the patients will be described in each group by the mean and the standard deviation, or by the quartiles and the minimum and maximum values according to the shape of the distribution. The qualitative characteristics of the patients will be described in each group by the absolute and relative frequency. The comparisons between the 3 groups will be carried out using an analysis of variance or the Kruskal Wallis test for the quantitative characteristics, and using the chi-2 test of homogeneity or the Fisher exact test for the qualitative characteristics.

2. Non-inferiority analysis

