The main analysis will be carried out in per protocol analysis. In this analysis, only the patients having received the assigned strategy will be considered. All patients with a major deviation to the protocol will be excluded. In the FIT group, the patients complying with at least one of the three screening rounds will be considered for per protocol analysis.

An analysis in intention to treat will also be conducted. In this analysis the patients will be analysed according to their randomisation group, irrespective of whether they will have received or not, the assigned strategy.

The proportion of patients detected with advanced neoplasia by the received strategy at the end of the three years of follow-up will be estimated in each group with its 95% confidence interval.

For each new strategy group (FIT or CCE), the difference of proportion between the group with new strategy and the reference group will be estimated with its 95% bilateral confidence interval. The method of the unilateral confidence interval of the difference will be used for non-inferiority testing. For each comparison, the unilateral alpha risk usually fixed at 5% for one comparison, will be halved and fixed at 2.5% in order to take into account that two comparisons will be carried out. The non-inferiority of the new strategy will be retained if the inferior bound of the confidence interval of the difference is superior to -3%.

3. Analysis for secondary objectives

The efficacy of each strategy for the detection of advanced neoplasia will be estimated on the patients who will have actually received the strategy, whatever their initial randomization group. It will be estimated by the proportion of detected patients at 3 years. They will be estimated with a 95% confidence interval and compared using a chi-2 test or a Fisher exact test.

The observed complications will be described in each group. The proportion of complications will be compared

between the three groups using a chi-2 test or a Fisher exact test.
A bilateral P-value ≤ 0.05 will be considered for statistical significance.
The methodology of the cost-effectiveness analysis is described in a specific paragraph.

STUDY DURATION / CALENDAR

This work needs a 7 years working period including:

- 6 months for study preparation
- 3 years of inclusion
- 3 years of follow-up for all patients before colonoscopy/end of study
- 6 months for data management and analysis, and publication

FEASIBILITY OF THE STUDY

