The efficacy of the two alternative strategies (colon capsule and FIT) for colon cancer and advanced adenoma detection has been mainly evaluated in average risk patient populations, which represents the main target for improving colorectal cancer detection. For this reason, data on the efficacy of colon capsule for the detection of cancer and advanced adenomas are lacking as these lesions are infrequent in average risk patients. Thus, this series, with an expected much higher frequency of advanced lesions will add major data on the feasibility of capsule endoscopy in colorectal cancer screening. On the other hand, the FIT strategy in high risk patients has been poorly studied and the efficacy of this method in this specific population is uncertain. This represents the second major knowledge improvement of the present study, and the value of the result will be high as a control group with colonoscopy will be used, and as a systematic control of missed lesions will be performed with optical colonoscopy.

If this study proves the non-inferiority of these 2 strategies as compared to optical colonoscopy, a major improvement of colorectal cancer screening can be expected in this population. Indeed, the main limitation of colorectal cancer screening in first degree relatives of patients with colorectal neoplasia is the acceptability rate of colonoscopy with a figure of about 40 % in published population-based studies. This limitation is responsible for colorectal cancer deaths. Alternative screening methods like FIT and colon capsule are expected to improve dramatically the acceptability of screening in this particular population, and this has to be proven by a second study.

Moreover, this high-risk group for colorectal cancer is a model for the general population and improving screening in the general population (acceptability rate is about 30% as a mean in France with Hemoccult[®] testing) is an even greater objective to reduce colorectal cancer death in developed countries. Data on the efficacy of alternative methods like the 2 methods proposed in this study will be a first step before a possible "multi option" screening strategy in order to improve, in the future, colorectal screening in the average risk/general population.

ETHICS AND REGULATORY PROCESS

Risk-Benefit for patients

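### The primary per-protocol rule can make membership of the main analysis set depend on the capsule or FIT result, because only test-negatives face the year-3 colonoscopy

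*Protocol*

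**What the plan says.** The Non-inferiority analysis section makes per protocol the main analysis: "In this analysis, only the patients having received the assigned strategy will be considered". Major deviations, which the protocol does not define, also lead to exclusion. One arm-specific relaxation is given: "In the FIT group, the patients complying with at least one of the three screening rounds will be considered for per protocol analysis". An intention-to-treat analysis is planned as well, but the non-inferiority conclusion is not made to depend on it.

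The strategy itself is defined under Study design: "2nd arm: CC first, OC at 3 years for those patients with negative initial CC". Patient follow-up and the objective of the medico-economic evaluation repeat this content. The FIT arm likewise ends with a year-3 colonoscopy for test-negatives. The OC arm has one colonoscopy and then telephone follow-up.

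The primary endpoint counts advanced neoplasia "or cancer identified by each strategy after 3 years", and the analysis section estimates "The proportion of patients detected with advanced neoplasia by the received strategy at the end of the three years of follow-up".

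Other passages describe the same year-3 examination as a check on the strategy. The first secondary endpoint mentions "or cancers detected at the end of the 3 years by control colonoscopy in arm 2 and 3", and the section on expected clinical value says "as a systematic control of missed lesions will be performed with optical colonoscopy".

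**The concern.** If the year-3 OC belongs to the assigned strategy, a capsule-negative patient who does not attend has not received that strategy and leaves the main analysis set. A capsule-positive patient cannot be excluded for this reason. Selection into the primary set would then depend on a post-randomisation test result, and only in the two experimental arms.

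Capsule-negatives have few or no advanced lesions. Removing them reduces the denominator by more, proportionally, than the numerator, so the CC proportion rises and CC minus OC moves toward non-inferiority. The FIT relaxation does not settle the matter: it concerns screening rounds, says nothing about the year-3 OC, and offers the CC arm nothing.

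**Working it through.** **Inputs from the protocol**
- Number of patients required: OC detection 6%, true difference 0, margin 3 points, one-sided 2.5% per comparison, 80% power, 984 per group, 10% loss to follow-up.
- Section 1.4: capsule sensitivity of 88% (larger polyps or adenomas, two smaller studies) to 92% (advanced adenoma, largest study).
- Risk-Benefit for patients: 30-40% of advanced lesions expected to be missed, so sensitivity 60-70%. This figure is not given separately for the capsule.

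**Assumptions not in the protocol**
- A share s of capsule-negatives skips the year-3 OC, independently of having a lesion. The main case is s = 10%, borrowed from the loss figure.
- Capsule positivity (pos) is 10-25%.
- Year-3 findings count as detected.
- For the main case, no capsule-positives and no OC patients are excluded.

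**1. The plan's own figure.** n = 2 × 0.06 × 0.94 × (1.960 + 0.842)² / 0.03² = 983.7, hence 984 per group. The sample size reproduces and is not in question.

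**2. Observed CC proportion under the literal rule.** With D = 0.06 and sensitivity S, the share kept is k = 1 − (1 − pos)s, and observed CC = D[S + (1 − S)(1 − s)] / k. At s = 10%:

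| S | pos | Numerator | k | Observed CC |
|---|---|---|---|---|
| 0.88 | 0.10 | 0.06 × (0.88 + 0.12 × 0.90) = 0.05928 | 0.910 | 6.51% |
| 0.92 | 0.10 | 0.06 × (0.92 + 0.08 × 0.90) = 0.05952 | 0.910 | 6.54% |
| 0.88 | 0.25 | 0.05928 | 0.925 | 6.41% |
| 0.92 | 0.25 | 0.05952 | 0.925 | 6.43% |

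The shift from 6.0% is 0.4-0.5 points, or 14-18% of the margin. With S = 0.60-0.70 the observed proportion is 6.2-6.4%.

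**3. Higher skip rates (assumptions only).** With S = 0.88-0.92, s = 20% gives 6.9-7.2% and s = 30% gives 7.5-8.0%.

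**4. Effect on the decision.** Suppose true CC detection is 3% (at the margin), 88% of it found by the capsule, positivity 10% and s = 10%. Observed CC = 0.03 × (0.88 + 0.12 × 0.90) / 0.91 = 3.26%, with 0.91 × 984 ≈ 895 patients. The unpooled standard error is √(0.0326 × 0.9674/895 + 0.06 × 0.94/984) = 0.0096. The chance of concluding non-inferiority is Φ(0.0026/0.0096 − 1.96) ≈ 4.5%, against the planned 2.5%.

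**5. When the shift disappears or reverses.**
- *Capsule-positives excluded at rate r.* Observed CC = D[S(1 − r) + (1 − S)(1 − s)] / [pos(1 − r) + (1 − pos)(1 − s)]. With r = s the factor (1 − s) cancels and the result is exactly 6.00%. With s = 10% and r = 15% it falls to 5.7-5.8%.
- *OC arm loses a share q of its negatives.* Observed OC = D/(1 − 0.94q), so break-even q = (1 − D/CC)/0.94. For CC of 6.41-6.54% this is about 7-9%. At q = 10%, OC = 0.06/0.906 = 6.62%, and CC minus OC is −0.21 to −0.08 points, against the capsule.

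**The case against.** The strongest reply is that the protocol never says a missed year-3 OC means the strategy was not received. Two passages call that examination a control. The secondary efficacy analysis groups patients by the strategy they actually received, and the FIT rule turns on screening rounds. A reading in which having the capsule is enough is therefore available, and the list of disqualifying deviations is often left to a statistical analysis plan, which is not at hand here. This stands as a reason to call the wording ambiguous. It does not remove the point: the protocol itself writes the per-protocol rule and, in several places, puts the year-3 OC inside the strategy.

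The second reply is that capsule-positives have a hurdle of their own. The endpoint needs histology, which a capsule cannot provide, so they must undergo a work-up colonoscopy to count as detected. The OC arm also has three years of telephone follow-up, and the 10% loss is not confined to any arm. This stands in full, and it makes the direction conditional.

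A reader might infer that the plan is biased toward non-inferiority, or that half to two-thirds of the margin is at risk. The documents support neither. The first needs unequal losses that the protocol does not predict. The second needs 30% skipping, three times the only loss figure given. The low colonoscopy uptake cited in the rationale is context from outside trials, not an estimate of year-3 attendance here.

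Finally, the planned intention-to-treat analysis would expose a discrepancy. That is true, but it does not govern the conclusion.

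**Conclusion.** The point holds as a conditional weakness in the wording of the primary analysis set. Read with the strategy definitions, the rule can exclude capsule-negatives and FIT-negatives for missing a step that test-positives do not have. At 10% skipping, with no matching loss among positives or in the OC arm, the CC proportion is overstated by 0.4-0.5 points. The size rests on assumed skip and positivity rates and on counting year-3 findings. The FIT effect was not sized. This should be corrected, with medium confidence: the text leaves the rule open, but it does not establish that the trial's result will be biased in either direction.

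**What to change.** **Per-protocol set.** Define membership in every arm by the initial screening test only: OC performed; capsule ingested and read; at least one FIT returned. State that membership does not depend on whether the year-3 OC, or the work-up of a positive test, took place. Patients without confirmation stay in the denominator as not detected.

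**Year-3 findings.** Reconcile Study design, Patient follow-up and the medico-economic objective with the first secondary endpoint and the expected-value section, and state whether year-3 OC findings count as detected by the strategy or are reported separately as missed lesions.

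**Cost.** Wording only, with no new data or patients. If year-3 findings count, keeping skippers is slightly conservative. CC detection becomes D[S + (1 − S)(1 − s)] over all 984. At 10% skipping this is 5.93-5.95% with sensitivity 88-92% (power about 78-79% instead of 80%) and 5.76-5.82% with sensitivity 60-70% (power 74-76%). If 10% of capsule-positives also went without work-up, detection would be 0.06 × 0.90 = 5.4%. The standard error would be √(0.054 × 0.946/984 + 0.06 × 0.94/984) = 0.0104, and power Φ(0.024/0.0104 − 1.96) ≈ 63%, so complete work-up of positives matters. If year-3 findings are reported separately, keeping skippers leaves the capsule count unchanged.

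As an optional safeguard, the protocol could require the intention-to-treat analysis to agree before non-inferiority is claimed.
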